13.8.1 Adverse Events

13.8.1.1 Definitions

All adverse events recorded during the study will be coded according to Medical Dictionary for Regulatory Activities.

13.8.1.2 Adverse Events

Summaries will be done for the following types of AE:

- Number (%) of patients with any AE,
- Number (%) of patients with any SAE,
- Number (%) of patients permanently withdrawn from treatment due to AE,

All summaries will display, by treatment group, the overall frequency of patients with events, the frequency of patients with events within each primary system organ class and by preferred terms. For each preferred term and each system organ class a patient will be counted only once. For summaries on severe or drug-related AE, for a given patient, the highest severity or relationship for a specific preferred term will be considered.

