11.2 Follow-up procedures after withdrawal

Patients who prematurely discontinue study drug are not to be replaced.

All randomized patients must be followed up according to the study flowchart until study end date or death, regardless of whether they discontinued study drug prematurely or not. Any event occurring after early study drug discontinuation will be recorded up through the study end date.

In case of study drug discontinuation (temporary or permanent) due to an adverse event, such patients will be closely monitored until the resolution or stabilization of this adverse event. This may mean that follow-up will continue after the patients have completed the study follow-up. Although data on that adverse event will continue to be captured, even

beyond the last visit, for new efficacy or safety events, only those that occur up through the last visit should be recorded.

In case of written withdrawal of consent (WOC) for follow-up visits, and unless otherwise stated by the patient in the informed consent form, Investigators will be encouraged to get information from the general practitioner, any other physician, or other medical-care provider, in order to follow the medical status of the patients (especially when they withdraw their consent after having experienced an AE/SAE or an efficacy endpoint). Investigators will also be expected to try as much as possible to re-contact those patients at the end of the trial, in order to obtain at least their vital status (dead or alive), as well as their stroke or MI status if possible, and thus avoid lost to follow-up for the efficacy assessment.

For patients considered lost to follow-up, the CRF must be completed up to the last visit performed.

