13.4.1.2 Populations to be analyzed

The intent-to-treat (ITT) population will be used for all efficacy and safety analyses. This will consist of all randomized patients irrespective of whether the patient actually received study drug or the patient's compliance with the study protocol, in the treatment group assigned by the IVRS system. A patient will be considered randomized as soon as a treatment kit number is assigned by IVRS.

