13.8 Safety analysis

For this morbidity/mortality trial, a benefit risk assessment is important. For this purpose safety analyses will be conducted on the same population (ITT) and using the same evaluation period as for efficacy analyses. (ie, from randomization until study end date)

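### AEs and SAEs are summarised only as percentages of all randomized patients, so a difference between arms in loss to follow-up would bias the safety comparison

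*Protocol*

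**What the plan says.** Section 13.8 gives benefit-risk assessment as the reason for its choice of population and period: "For this purpose safety analyses will be conducted on the same population (ITT) and using the same evaluation period as for efficacy analyses". Section 13.4.1.2 names the population, "The intent-to-treat (ITT) population will be used for all efficacy and safety analyses", and defines it as all randomized patients, whether or not they took drug or complied.

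Section 13.8.1.2 then lists the summaries. They include "Number (%) of patients with any AE" and "Number (%) of patients with any SAE". One display is fixed for the whole list: "All summaries will display, by treatment group, the overall frequency of patients with events". Each patient counts once per preferred term and once per system organ class. Sections 13.8.1.3 and 13.8.1.4 summarise SAEs, events leading to death and AEs leading to discontinuation by the same classes. None of these sections uses follow-up time. The only person-time in section 13 is patient-years on study drug (13.6.1.1), an exposure summary not linked to AE counts.

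On data capture, section 11.2 says: "For patients considered lost to follow-up, the CRF must be completed up to the last visit performed". After withdrawal of consent, investigators are encouraged to seek information from other physicians. They are also expected to attempt one more contact when the trial closes. The stated aim of that contact is limited: "in order to obtain at least their vital status (dead or alive), as well as their stroke or MI status if possible". Section 13.4.2.1 rules out imputation in general. For efficacy, section 13.7.1.2.1 censors patients without an event at their last assessment, and section 13.7.1.2.3 uses Kaplan-Meier curves and a log-rank test.

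**The concern.** A patient lost at month 12 with no recorded SAE stays in the denominator and counts as event-free to the study end date, which may be three years later. The crude percentage is therefore at most what full follow-up would give, and the shortfall grows with the amount of loss. If both arms lose patients at the same rate, the two percentages fall together and their ratio hardly moves. If one arm loses more, its percentage falls further.

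Safety is a named objective (section 5.3), and 13.8 says its tables are meant for weighing benefit against risk. If the arm with more adverse events also lost more patients, part of a real excess would not show. If the other arm lost more, the excess would look too large. This is a separate matter from on-treatment versus intent-to-treat reporting, because it arises within the intent-to-treat period itself.

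**Working it through.** **Figures in the plan.** The AE sections give no number to reproduce. The follow-up assumption can be checked against section 13.2: 8,500 per arm, 17 months of uniform accrual, 50 months in total, 3% per year on placebo and a 15% reduction. Exponential event times give 1,554 expected events if 3% is a hazard and 1,577 if it is an annual risk, against about 1,600 stated. So follow-up of 33 to 50 months, mean 41.5 months or 3.458 years, is a sound reading.

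**Inputs that are assumptions.** The protocol states no SAE rate, no loss rate and no difference in loss. Assumed here: an SAE hazard r of 5% per year, a fraction l of patients whose AE reporting ends at month 12, and loss unrelated to SAE risk. Death is ignored.

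**Formula.** Crude % = (1 − l)(1 − exp(−3.458 r)) + l(1 − exp(−r)).

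At r = 0.05 the two risks are 15.88% (full follow-up) and 4.88% (12 months).

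- l = 8%: 0.92 × 15.88 + 0.08 × 4.88 = 15.0%
- l = 12%: 0.88 × 15.88 + 0.12 × 4.88 = 14.6%
- l = 15%: 0.85 × 15.88 + 0.15 × 4.88 = 14.2%

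| Lost, placebo vs rimonabant | True HR | Crude % | Crude ratio |
|---|---|---|---|
| equal | 1.00 | equal | 1.00 |
| 8% vs 12% | 1.00 | 15.0 vs 14.6 | 0.97 |
| 8% vs 15% | 1.00 | 15.0 vs 14.2 | 0.95 |
| 10% vs 20% | 1.00 | 14.8 vs 13.7 | 0.93 |
| 8% vs 8% | 1.10 | 15.0 vs 16.4 | 1.09 |
| 8% vs 15% | 1.10 | 15.0 vs 15.5 | 1.035 |

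In the last two rows the fair comparator is 1.09, not 1.10. A hazard ratio of 1.10 already becomes a risk ratio of 1.09 under equal loss, so differential loss accounts for the step from 1.09 to 1.035.

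**Rate on the same data.** With a constant hazard, expected follow-up to first SAE is the crude risk divided by r. For 8% vs 15% lost and no true difference this is 0.150/0.05 = 3.00 and 0.1423/0.05 = 2.85 years per patient. Both arms then show 5.0 first events per 100 patient-years, ratio 1.00. With a true HR of 1.10 the rates are 5.0 and 5.5, ratio 1.10.

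**A second loss model.** Here loss occurs at a constant rate c, follow-up F is uniform over 33 to 50 months, the placebo SAE hazard is 3% per year and placebo loss is 1% per year. With SAE hazard λ in an arm, crude risk is the mean over F of [λ/(λ + c)](1 − exp(−(λ + c)F)).

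| Loss per year in the active arm | Crude ratio, true HR 1.25 | Crude ratio, true HR 1.00 |
|---|---|---|
| 1% | 1.23 | 1.00 |
| 2% | 1.21 | 0.98 |
| 3% | 1.19 | 0.97 |
| 5% | 1.15 | 0.93 |

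With the losses reversed (5% placebo, 1% active), a true HR of 1.25 shows as 1.32. The ratio per patient-year is 1.25, or 1.00, in every case.

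**The case against.** The strongest objection is that patient-year rates and cumulative incidence displays are ordinary SAP content, and the SAP is not at hand. Section 13.1 calls section 13 the basis for that plan, and the listed summaries do not forbid others. The SAP may therefore already supply what is missing. But the protocol does more than stay silent: 13.8.1.2 prescribes what every AE summary will show, and that statistic ignores unequal observation. The point stands as an improvement to the protocol's wording, and falls away if the SAP adds the rates.

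A reader might infer that 13.8 breaks its own promise of a common basis for benefit and harm. It does not. It promises the same population and period, not the same estimator, and 13.7.1.2.3 also reports the primary endpoint as a crude number and percentage.

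A reader might also take the 10% annual discontinuation rate in 13.2 as the rate at which AE data are lost. Section 11.2 rules this out, because patients who stop drug are followed on the full schedule. Section 12.3 requires a final visit for everyone, with contact attempts recorded. Sections 11.2 and 11.3 encourage medical follow-up through other physicians after withdrawal of consent. That reduces the gap but does not secure capture of new AEs.

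Three further limits stand. An AE that prompts a patient to leave will usually have been recorded first, so AEs leading to permanent withdrawal of treatment are barely affected. All-cause mortality and the cardiovascular endpoints are analysed by time to event (13.7.2.2), and the primary and secondary endpoints are not counted as AEs (10.3). Finally, rates per patient-year also assume uninformative loss, so they remove the bias from unequal observation time but not bias from loss related to AE risk.

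**Conclusion.** The point holds in conditional form. The protocol fixes a crude percentage of all randomized patients for AEs and SAEs, while AE observation can end early in lost or withdrawn patients. The resulting comparison is biased only if those losses differ between arms, and then towards fewer events in the arm with more loss. The documents do not support saying that harm will be understated in this trial, or in which arm.

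The size rests wholly on assumed rates. At an SAE hazard of 5% per year the crude ratio under no true difference is 0.97 for 8% versus 12% lost at month 12 and 0.95 for 8% versus 15%. A true HR of 1.10 shows as 1.035 instead of 1.09 in the latter case. At yearly losses of 1% versus 2% the shift is about 0.02, and with equal loss it is about nil. It is a cheap improvement worth making, with medium confidence.

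**What to change.** Keep the numbers and percentages in 13.8.1.2 to 13.8.1.4 and add:

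- For any SAE, and for AEs by system organ class and preferred term, first events per 100 patient-years of AE follow-up. Time runs from randomization to the first such event, the last contact at which AEs were assessed, death or the study end date, whichever comes first. Patient-years on study drug are not the right denominator, because the evaluation period includes time off drug.
- For any SAE, cumulative incidence by arm, with a death that is not itself counted as an SAE treated as a competing event. Under section 10.3 this applies to cardiovascular deaths, which are endpoints and not AEs. A plain Kaplan-Meier curve that censors these deaths would overstate the incidence.
- AE follow-up time and losses to AE follow-up, by arm, so that the reader can judge whether the percentages are comparable.

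The cost is a few sentences and some table columns. AEs are asked about at every visit and phone call (9.2, 12.3), so the contact dates should come from existing CRF pages. The downside is that a rate per patient-year averages over time and assumes uninformative loss, which is why the percentages stay beside it.

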13.8.1.3 Deaths and Serious Adverse Events

Serious adverse events and events leading to death (non-CV deaths) will be summarized overall and by primary system organ class and preferred term.

13.8.1.4 Adverse Events leading to treatment discontinuation

Adverse events leading to treatment discontinuation will be summarized overall and by primary system organ class and preferred term.

13.8.2 Clinical laboratory evaluations

The analysis will focus on potentially clinically significant abnormality (PCSA) values. Patients with PCSA for each test will be identified. Number and percentage of patients with PCSA at any post-randomization time point will be used to summarize each clinical laboratory test. The summaries will include patients who have at least one laboratory test performed after the first study drug administration and, when required by the definition of the abnormality, with an available baseline value. For these descriptions the baseline value will be the last available measure before study drug intake.

Descriptive statistics will also be used to summarize the values and changes from baseline for each treatment group across time.

13.8.3 Vital signs

Assessment of vital signs will be carried out as described in [Section 13.8.2](#).

14. SUBSTUDIES

There will be a Metabolic Substudy conducted in selected sites, encompassing approximately 3000 patients. This substudy will assess rimonabant's effects on fasting plasma glucose, insulin, HbA1c, triglyceride, HDL-cholesterol, and LDL-cholesterol levels compared to placebo, in a subset of CRESCENDO patients. Samples will be obtained at baseline and every six months thereafter, and at the End of Study visit. This study will be the subject of a separate protocol ([Appendix 9](#)) and informed consent.

Other substudies of high scientific merit will be conducted based on the recommendation of the Executive Committee. Substudies planned include a Biomarker Substudy and a Genomics Substudy. These studies will be the subject of separate protocols ([Appendix 10](#) and [Appendix 11](#)) and informed consents.

The analysis and reporting of the substudies will be totally separate from the main study.

15. ETHICAL AND REGULATORY STANDARDS

15.1 Ethical principles

This Clinical Trial will be conducted in accordance with the principles laid down by the 18th World Medical Assembly (Helsinki, 1964) and all applicable amendments laid down by the World Medical Assemblies, and the ICH guidelines for Good Clinical Practice (GCP). Those Investigators participating as leaders in this trial, including members of the Executive and Operations Committees and National Coordinators, will receive compensation for their time but will receive no financial profit from their activities related to the trial.

15.2 Laws and regulations

This Clinical Trial will be conducted in compliance with all international laws and regulations, and national laws and regulations of the countries in which the clinical trial is performed, as well as any applicable guidelines. The trial will be registered on www.clintrials.gov and on other sites, as appropriate.

15.3 Informed consent

The Investigator (according to applicable regulatory requirements), or a person designated by the Investigator, and under the Investigator's responsibility, should fully inform the patient of all pertinent aspects of the clinical trial, including the written information given approval/favorable opinion by the Institutional Review Board/Ethics Committee (IRB/EC).

Prior to a patient's participation in the clinical trial, the written Informed Consent Form should be signed, name filled in and personally dated by the patient or by the patient's legally acceptable representative, and by the person who conducted the informed consent discussion. A copy of the signed and dated written Informed Consent Form will be provided to the patient.

If informed consent is obtained under special circumstances (emergency, from a guardian, minor, etc.), the method should be specified following the ICH requirements. The first part of the section should be adapted, keeping the point as appropriate.

The Informed Consent Form used by the Investigator for obtaining the patient's informed consent must be reviewed and approved by the Sponsor prior to submission to the appropriate IRB/EC for approval/favorable opinion.

15.4 Institutional Review Board/Independent Ethics Committee (IRB/EC)

The Investigator must submit this Clinical Trial Protocol to the appropriate IRB/EC, and is required to forward to the Sponsor a copy of the written and dated approval/favorable opinion signed by the Chairman with IRB/EC composition.

The Clinical Trial (study number, Clinical Trial Protocol title and version number), the documents reviewed (Clinical Trial Protocol, Informed Consent Form, Investigator's Brochure, Investigator's CV, etc.) and the date of the review should be clearly stated on the written IRB/EC approval/favorable opinion.

Investigational Product will not be released at the study site and the Clinical Trial will not start until a copy of this written and dated approval/favorable opinion has been received by the Sponsor.

During the Clinical Trial, any amendment or modification to the Clinical Trial Protocol should be submitted to the IRB/EC. It should also be informed of any event likely to affect the safety of patients or the continued conduct of the Clinical Trial, in particular any change in safety. All updates to the Investigator's Brochure will be sent to the IRB/EC.

If requested, a progress report is sent to the IRB/EC annually and a summary of the Clinical Trial's outcome at the end of the Clinical Trial.

16. STUDY MONITORING

16.1 Responsibilities of the Investigator(s)

The Investigator(s) undertake(s) to perform the Clinical Trial in accordance with this Clinical Trial Protocol, ICH guidelines for Good Clinical Practice and the applicable regulatory requirements.

The Investigator is required to ensure compliance with all procedures required by the Clinical Trial Protocol and by study procedures provided by the Sponsor (including security rules). The Investigator agrees to provide reliable data and all information requested by the Clinical Trial Protocol (with the help of the Case Report Form [CRF], Discrepancy Resolution Form [DRF] or other appropriate instrument) in an accurate and legible manner according to the instructions provided and to ensure direct access to source documents to Sponsor representatives.

If any particular circuits have to be defined (e.g., e-CRF, Fax), particular attention should be paid to the confidentiality of the patient's data to be transferred.

The Investigator may appoint such other individuals as he/she may deem appropriate as Sub-Investigators to assist in the conduct of the Clinical Trial in accordance with the Clinical Trial Protocol. All Sub-Investigators shall be timely appointed and listed. The Sub-Investigators will be supervised by and under the responsibility of the Investigator. The Investigator will provide them with a Clinical Trial Protocol and all necessary information.

16.2 Responsibilities of the Sponsor

The Sponsor of this Clinical Trial is responsible to Health Authorities for taking all reasonable steps to ensure the proper conduct of the Clinical Trial Protocol as regards ethics, Clinical Trial Protocol compliance, integrity and validity of the data recorded on the Case Report Forms. Thus, the main duty of the Monitoring Team is to help the Investigator and the Sponsor maintain a high level of ethical, scientific, technical and regulatory quality in all aspects of the Clinical Trial.

At regular intervals during the Clinical Trial, the site will be contacted, through monitoring visits, letters or telephone calls, by a representative of the Monitoring Team to review study progress, Investigator and patient compliance with Clinical Trial Protocol requirements, and any emergent problems. During these monitoring visits, the following but not exhaustive list of points will be scrutinized with the Investigator: patient informed consent, patient recruitment and follow-up, Serious Adverse Event documentation and reporting, outcome events documentation and reporting, Investigational Product allocation, patient compliance with the Investigational Product regimen, Investigational Product accountability, concomitant therapy use and quality of data.

16.3 Source document requirements

According to the ICH guidelines for Good Clinical Practice, the Monitoring Team must check the Case Report Form entries against the source documents, except for the pre-identified source data directly recorded in the Case Report Form. The Informed Consent Form will include a statement by which the patient allows the Sponsor's duly authorized personnel, the Ethics Committee (IRB/EC), and the regulatory authorities to have direct access to source data which supports the data on the Case Report Forms (e.g., patient's medical file, appointment books, original laboratory records, etc.). These personnel, bound

by professional secrecy, must keep confidential all personal identity or personal medical information (according to confidentiality rules).

16.4 Use and completion of Case Report Forms (CRFs) and additional requests

It is the responsibility of the Investigator to maintain adequate and accurate CRFs designed by the Sponsor to record all observations and other data pertinent to the clinical investigation. All CRFs should be completed in their entirety in a neat, legible manner to ensure accurate interpretation of data; a black ball point pen should be used to ensure the clarity of the reproduced copy of all CRFs, which should be faxed within 48 hours of completion or any modification to the Central Database number.

Should a correction be made, the information to be modified must not be overwritten. The corrected information will be transcribed by the authorized person next to the previous value, initialed and dated, and the corrected CRF should be faxed again to the Central Database number.

The computerized handling of the data by the Sponsor after receipt of the CRFs may generate additional requests (DRF) to which the Investigator is obliged to respond by confirming or modifying the data questioned. Unresolved requests will be faxed to the Investigator at least every 2 weeks. Modified CRFs following resolution of the queries should be faxed again to the Central Database number.

17. ADMINISTRATIVE RULES

17.1 Curriculum Vitae

An updated copy of the curriculum vitae limited to the experience, qualification and training for each Investigator and Sub-Investigator will be provided to the Sponsor prior to the beginning of the Clinical Trial.

17.2 Record retention at study site(s)

The Investigator must maintain confidential all study documentation, and take measures to prevent accidental or premature destruction of these documents.

It is recommended that the Investigator retain the study documents at least fifteen (15) years after the completion or discontinuation of the Clinical Trial.

However, applicable regulatory requirements should be taken into account in the event that a longer period is required.

The Investigator must notify the Sponsor prior to destroying any study essential documents within the fifteen (15) year period following the Clinical Trial completion or discontinuation.

If the Investigator's personal situation is such that archiving can no longer be ensured by him/her, the Investigator shall inform the Sponsor and the relevant records shall be transferred to a mutually agreed upon designee.

